- g On Day 1 and Day 15 of every cycle, vital signs (blood pressure, pulse, respiratory rate, temperature) will be assessed predose (within 15 min of oral dosing after the subject has rested in the semi-recumbent position for 3 to 5 min), and then every 15 min from dosing of M4112 for an additional 2 h. Observation can be extended per investigator's discretion. Height and weight at Screening only.
- h For ECG time points of safety monitoring: Standard triplicate (within 2 min) digital 12-lead ECG will be obtained after the subject has been rested in semi-recumbent position for at least 5 min at Screening, predose and 2, 3, 4 and 8 h postdose on Days 1 and 15 of Cycle 1, predose on Day 8 of Cycle 1, and on Day 1 Cycle 2 (and + 2 h postdose), Day 1 Cycle 4, Day 1 Cycle 6 and then every second cycle thereafter at predose and at least 60 min postdose on these visits. ECGs will be also performed during the End of Treatment and Safety Follow-up Visit (30  $\pm$  3 days). Triplicate ECGs will be read locally. The calculated QTc average of the three 12-lead ECGs must be  $\leq$  450 ms for continued eligibility. Subjects, in which the calculated QTc average increases to  $>$  500 ms or  $>$  60 ms change over baseline during treatment with M4112, have to interrupt study treatment until further clinical evaluation of QT prolongation. During single agent dose escalation (Part IA), replicate digital 12-lead ECGs within 2 min after a minimum of 5 min rest in semi-recumbent position will also be collected on Days 1 and 15 of Cycle 1 for concentration-QTc analysis, for time points, see Table 4. For Part 1A only, replicate ECGs (Holter) will also be collected on Days 1 and 15 of Cycle 1 for exposure-QTc analysis.
- i Hematology includes complete blood count with differential and platelet counts. Blood samples for hematology will be obtained prior to administration of study drug (see Table 10).
- j Coagulation with aPTT and prothrombin time. Blood samples will be collected prior to administration of study drug (see Table 10).

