ECG = Electrocardiogram; eCRF = electronic case report form; **CCI** [REDACTED]; **CCI** [REDACTED]; PBMC = peripheral blood mononuclear cell; PD = pharmacodynamics; PK = pharmacokinetics; QTc = corrected QT interval; **CCI** [REDACTED].

- a Including optional metabolite analysis from samples. For all study medication administration, a physician must be present at the site or immediately available to respond to emergencies during all administrations. Critical care and resuscitation facilities should be available immediately.
- b Actual collection times should be collected in the eCRF along with the times of the last dose administration.
- c For subjects in single M4112 dose escalation:  
QTc monitoring: In addition to the ECGs collected for safety monitoring, subjects will undergo replicate (at least 3) digital 12-lead ECGs after a minimum of 5 min rest in the semi-recumbent position on Cycle 1 at Day 1 and Day 15 at -45, -30 and -15 min predose and at 0.5, 1, 2, 3, 4, 6 and 8 postdose. ECG recordings must be performed before PK sampling time points. Time points may change if  $C_{max}$  is not as predicted.
- d Predose = approximately 12 ( $\pm$  4) h post the last evening dose.
- e Predose replicate readings will be collected -45, -30 and -15 min predose; a triplicate digital 12-lead ECG will also be collected predose (within 30 min) for local reading.
- f In addition, standard digital triplicate (within 2 min) 12-lead safety ECGs are to be collected predose and at 2, 3, 4 and 8 h postdose on Days 1 and 15 and predose on Day 8 during Cycle 1, and predose and + 2 h postdose on Day 1 Cycle 2. Safety ECGs will be read locally and **all ECGs should be assessed on the day of collection to determine continued eligibility**. The calculated QTc average of the triplicate 12-lead ECGs must be  $\leq$  450 ms for eligibility. Subjects, in which the calculated QTc average increases to  $>$  500 ms or  $>$  60 ms change over baseline during treatment with M4112, have to interrupt study treatment until further clinical evaluation.  
**ECGs should be repeated if QTc is outside the range until resolution.** To assess the safety and tolerability of the IMP, an ECG can be repeated at the Investigator's discretion at unscheduled visits. Start of resting time, ECG time, and PK sampling time will be recorded in the eCRF. Day 1 and Day 15 triplicate digital ECGs will be also be uploaded for summary statistics, outlier and exposure-QTc analyses.

CCI

CCI

CCI

CCI

CCI

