- Subjects who experience an increase in QT: Subjects in which the calculated QTc average (using the Fridericia correction calculation) increases to  $> 500$  ms on any triplicate reading or  $\geq 60$  ms change over baseline during treatment with M4112 have to interrupt study treatment until further clinical evaluation.

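### The protocol ties continued eligibility to a QTc of at most 450 ms without saying what follows when that is exceeded on treatment, and it writes the 60 ms interruption trigger two ways

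*Protocol*

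**What the plan says.** - **Protocol Table 1, footnote h.** The footnote lists safety ECGs from Screening through the treatment cycles to Safety Follow-up. The average of the three tracings must be no more than "450 ms for continued eligibility". The next sentence acts when the average exceeds 500 ms or shows more than a "60 ms change over baseline during treatment with M4112, have to interrupt study treatment until further clinical evaluation of QT prolongation".
- **Protocol Table 4, footnote f.** It states that "all ECGs should be assessed on the day of collection to determine continued eligibility". It then sets the triplicate average at no more than "450 ms for eligibility" and repeats the triggers of more than 500 ms or more than 60 ms. It adds "ECGs should be repeated if QTc is outside the range until resolution", without defining the range.
- **Protocol Section 6.2.3, last rule before Section 6.2.4.** Its subject is the calculated QTc average, Fridericia-corrected. It acts above 500 "ms on any triplicate reading or" at 60 or more "ms change over baseline during treatment with M4112 have to interrupt study treatment until further clinical evaluation". It contains no 450 ms limit.
- **Protocol Section 5.3.2, exclusion criterion 6.** QTc above 450 ms excludes a subject at entry.
- **Protocol Section 5.5.1.** When an exclusion criterion arises on treatment, withdrawal depends on clinical relevance, effect on safety, and the judgement of the investigator or sponsor.

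**The concern.** Section 3.4.2.1 names QT/QTc prolongation as an important potential risk in this first-in-human study and relies on entry and withdrawal criteria to control it. Those criteria need to give one answer for a given ECG. As written, a site reading the 450 ms sentence may conclude that a subject at 470 ms is no longer eligible. A site reading the next sentence, or Section 6.2.3, may see no reason to interrupt.

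The choice matters for the subject, because Section 6.2.3 makes discontinuation permanent once a treatment delay exceeds 2 weeks. It also matters for judging deviations consistently, since a deviation cannot be classified against a rule with two readings.

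**Working it through.** The documents give no figure to reproduce. The check sets the three rules side by side and then finds the QTc values on which they fail to agree.

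| | Table 1 footnote h | Table 4 footnote f | Section 6.2.3 |
|---|---|---|---|
| 450 ms limit | yes, for continued eligibility | yes, for eligibility; all ECGs checked the same day | absent |
| Absolute trigger | > 500 ms | > 500 ms | > 500 ms |
| Change trigger | > 60 ms | > 60 ms | ≥ 60 ms |
| Value used | average of three | average of triplicate | calculated average, then any triplicate reading |
| Correction | not named | not named | Fridericia |

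**Where the limit is failed but no trigger is met.** Let B be the baseline QTc and Q the on-treatment average, in ms.

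- The 450 ms limit is failed if Q > 450.
- The footnotes interrupt if Q > 500 or Q − B > 60.
- The gap is therefore 450 < Q ≤ min(500, B + 60).
- It exists only if B + 60 > 450, that is, B > 390.
- Its width is min(50, B − 390).

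Criterion 6 caps entry QTc at 450 ms, so B is taken up to 450. In whole milliseconds:

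| Baseline | Gap, footnotes (> 60) | Gap, Section 6.2.3 (≥ 60) |
|---|---|---|
| 380 | none | none |
| 390 | none | none |
| 400 | 451–460 | 451–459 |
| 410 | 451–470 | 451–469 |
| 420 | 451–480 | 451–479 |
| 430 | 451–490 | 451–489 |
| 440 | 451–500 | 451–499 |
| 450 | 451–500 | 451–500 |

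The order can also reverse. At a baseline of 380 ms, values of 441 to 450 ms satisfy the 450 ms limit, yet the rise is 61 to 70 ms and interruption is required.

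**Change trigger.** At a rise of exactly 60 ms (for example 400 to 460 ms), the footnotes do not interrupt because 60 is not greater than 60. Section 6.2.3 does, because 60 ≥ 60.

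**Averaging.** Take an assumed triplicate of 505, 495 and 494 ms. The mean is (505 + 495 + 494) / 3 = 1,494 / 3 = 498 ms, so the average does not exceed 500 ms. If any single tracing counts, 505 ms does.

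**The case against.** The strongest reply is that 450 ms is an entry limit. Exclusion criterion 6 uses the same figure. Table 1 footnote e has the criteria reviewed again before dosing on Cycle 1 Day 1, so eligibility can be continued from Screening to Day 1. Only the 500/60 ms sentence is expressly limited to the treatment period, and footnote f's own 450 ms sentence says eligibility without the word continued.

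This reading is possible, but the text does not settle on it. Table 4 covers Cycle 1 and Cycle 2 Day 1 with no Screening row. Every time point marked f in the table follows the first dose, although the wording of footnote f also mentions Day 1 predose. The same-day check applies to all ECGs.

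Four stronger readings are tempting and are not supported:

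- **A stop order from 451 to 500 ms.** A reader might infer opposite instructions across a fixed 50 ms band. No passage orders a stop in that range, and Section 5.5.1 leaves withdrawal to judgement. The full band exists only at baselines of 440 to 450 ms. Nor does interruption start only above 500 ms, since the 60 ms trigger can act first.
- **A proven averaging conflict.** The grammatical subject in Section 6.2.3 is the calculated average, and Section 7.2.6 treats mean QTc as the average of triplicates. The phrase may mean the average of any triplicate set. This is an ambiguity.
- **Lost DLT evaluability.** Sections 5.1, 6.2.4 and 8.5.2 exclude subjects only for doses missed for other than safety reasons, and a QTc interruption is a safety reason. The IAP's DLT set requires only 5 total daily doses received, or a DLT. Protocol Table 13, which excepts only DLTs, leaves some room, but the IAP has since updated that definition. An effect on the QTc outlier analysis is conceivable, but the documents give no basis for sizing it.
- **A clash with IAP Table 6.** Its QTcF categories are descriptive reporting bins. They need not match interruption triggers.

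**Conclusion.** The inconsistency stands in two parts. First, the scope and consequence of the 450 ms limit are unstated. This leaves up to 50 ms unresolved, depending on baseline: nothing at 390 ms or below, 10 ms at 400, 30 ms at 420, and 50 ms at 440 to 450. Second, a rise of exactly 60 ms requires interruption under Section 6.2.3 and not under the footnotes.

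The averaging phrase and the absence of a named correction in the footnotes are lesser ambiguities in the same rule. The range calculation assumes whole-millisecond averages, a baseline no higher than the entry limit, and the same correction formula at baseline and on treatment. The documents give no distribution of baseline QTc, so how many subjects fall in the unresolved range cannot be estimated.

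**What to change.** Reconcile Table 1 footnote h, Table 4 footnote f and Section 6.2.3, together with their relation to exclusion criterion 6 and Section 5.5.1, into one rule cited from each place. It should state:

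1. whether the 450 ms limit applies at entry only or also on treatment and, if on treatment, what follows when it is exceeded;
2. one inequality for the change from baseline;
3. one averaging convention, making clear whether a single tracing can trigger action;
4. one correction formula;
5. what range footnote f means when it calls for repeat ECGs.

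Which thresholds to keep is for the sponsor and clinical team. IAP Table 6 needs no change. The cost is a protocol clarification, with no added assessments.

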## Sponsor, Investigators and Study Administrative Structure

The Sponsor of this clinical study is EMD Serono Research & Development Institute, Inc., Billerica, MA, in the US and Canada and Merck KGaA, Darmstadt, Germany, in the rest of the world.

The study will be conducted at approximately 3 to 5 sites in the US for the dose escalation part (Part 1).

A contract research organization (CRO), PPD will undertake the operational aspects of this study. Details of such structures and associated procedures will be defined in a separate Integrated Project Management Plan maintained by PPD. The Integrated Project Management Plan will be prepared by the PPD Clinical Project Manager in cooperation with other PPD operational team leads.

The Sponsor will coordinate the study and will utilize the support of the CRO for the management of most activities of the study. Sponsor will perform oversight of the activities performed by the CRO.

The study will appear in the following clinical study registry: ClinicalTrials.gov and other applicable registries.

The Coordinating Investigator represents all Investigators for decisions and discussions regarding this study, consistent with the International Council for Harmonization (ICH) Topic E6 Good Clinical Practice (GCP). The Coordinating Investigator will provide expert medical input and advice relating to study design and execution and is responsible for the review and signoff of the clinical study report.

Signature pages for the Protocol Lead and the Coordinating Investigator as well as a list of Sponsor responsible persons are provided in [Appendix VI](#).

The Clinical Study Supplies department of the Sponsor will supply the study medication of CCI M4112, and CCI to the sites.

Safety laboratory assessments will be performed locally. Results from these local laboratories will be recorded according to the electronic case report form (eCRF) completion guidelines.

Pharmacokinetic (PK), CCI (central laboratory), and CCI assessments will be performed under the responsibility and/or supervision of the Sponsor.

The Drug Safety department, Merck KGaA, Darmstadt, Germany, or their designated representatives will supervise drug safety and the timely reporting of adverse events (AEs) and serious adverse events (SAEs).

Monitoring and data management will be performed by PPD, and the Sponsor will be responsible for regulatory submission.

Quality assurance of the study conduct will be performed by the Development Quality Assurance Department, Merck KGaA, Darmstadt, Germany.

PPD will write the study statistical analysis plan, perform the statistical analyses, and will provide the outputs from the statistical analyses. The Sponsor's department of Global Biostatistics will supervise the statistical analyses.

## 2.1 Safety Monitoring Committee

A Safety Monitoring Committee (SMC) will review the safety data on a regular basis. The SMC consists of members of the Sponsor (Drug Safety Product Leader, Medical Responsible, Clinical Pharmacologist and Biostatistician), the CRO (Medical Responsible) and the Coordinating Investigator. Ad hoc members may be invited as needed. During the dose-escalation part of the study, the SMC will evaluate the safety, tolerability, pharmacokinetics (PK) and available CCI

Based primarily on dose-limiting toxicities (DLTs), the SMC will advise on dose escalation, dose de-escalation, dose expansion, change in administration schedule/regimen (change for example from twice daily [BID] to once daily [QD]), or recommend suspension of enrollment, with the final adjudication being a Sponsor decision. The SMC will recommend the starting dose for M4112 CCI based on the observed safety, tolerability, available PK and PD markers of M4112 as single agent CCI. The SMC will decide, by consensus, on continuation of the study, or recommend modification or suspension of the study, with the final adjudication being a Sponsor decision. During the course of the study, the SMC may modify the frequency of its meetings as deemed appropriate. In cases where enrollment of the last subject in a dosing cohort was delayed, the SMC may decide (based on available data) upon enrollment and dose for the next dosing cohort before all subjects in a cohort have completed Cycle 1. Subjects will be assigned sequentially to cohorts of either M4112 as a single agent, CCI

[figure not shown]
The specific working procedures will be described in an SMC charter, which will be established prior to the start of recruitment.

## 3 Background Information

Immunotherapy has shown encouraging response rates in different solid tumors, however, the majority of subjects will not receive significant benefit from these agents, suggesting the existence of additional immunoregulatory pathways.

CCI

CCI

CCI

CCI

CCI

### 3.1 M4112

#### M4112 Pharmacology in Animal Models

M4112 (also known as MSC2579448) is an orally available small molecule inhibitor of the immunoregulatory metabolic enzymes indoleamine 2,3-dioxygenase 1 (IDO1) and tryptophan 2,3-dioxygenase (TDO2) (41). **CC1**

CCI

CCI

CCI

CCI

CCI

CCI

CCI

CCI

3.3

CCI

CCI

CCI

CCI

CCI

CCI

CCI

[figure not shown]
CCI

CCI

[figure not shown]
CCI

CCI

[figure not shown]
CCI

- CCI

- CCI

CCI

CCI

CCI

### 3.4 Rationale for the Current Clinical Study and Overall Benefit and Risk Considerations

Refer to the IB for further information about the nonclinical and clinical programs and guidance for the Investigator.

This clinical study will be conducted in compliance with the clinical study protocol, ICH GCP, and any additional applicable regulatory requirements.

Based on the available nonclinical and clinical data to date, the conduct of the study specified in this protocol is considered justifiable.

#### 3.4.1 Rationale for the Current Clinical Study

The purpose of this study is to evaluate the safety, tolerability, PK, PD, and preliminary efficacy of M4112 as single agent. CCI 2 immune checkpoint inhibitors with distinct modes of action, in subjects with proven advanced or metastatic solid malignancies for whom no effective standard therapy exists or has failed or subjects who are intolerant to established therapy known to provide clinical benefit for their condition. The dose escalation part of the study will establish the RP2D of M4112 as single agent CCI .

The administration of M4112 to subjects with advanced solid tumors for whom no approved/established effective treatment option exists is justified by the following:

- M4112 is a dual IDO1/TDO2 inhibitor able to inhibit immune suppression in vitro when administered as a monotherapy and with enhanced efficacy CCI with immune check point inhibitors in animal models

[REDACTED]

CCI

[REDACTED]

CCI

[REDACTED]

CCI

[REDACTED]

CCI

[REDACTED]

Together, these findings suggest that M4112, CCI [REDACTED], may have the potential to be an effective anticancer therapy and thus support its clinical development.

### 3.4.2 Overall Risk-Benefit Assessment

The administration of M4112 to subjects with advanced solid tumors for whom no approved/established effective treatment option exists is justified by the following:

- M4112 is a dual IDO1/TDO2 inhibitor able to inhibit immune suppression in vitro when administered as a monotherapy and with enhanced efficacy in preclinical models [REDACTED]
- Clinical experience with IDO1 inhibitor agents described in the literature demonstrate an acceptable safety profile as single agent [REDACTED] CCI [REDACTED] and encouraging clinical antitumor activity in solid tumors in Phase I studies.

- CCI

IDO1/TDO2 are key regulators of adaptive and innate immunity. CCI [REDACTED]

This clinical study will be conducted in compliance with the regulations of ICH GCP, and any additional applicable regulatory requirements.

The safety monitoring and reporting as well as risk management and mitigation measures inherent to early phase clinical studies in oncology patients are considered adequate for this study.

#### 3.4.2.1 Risk-Benefit Ratio of M4112

The **risk-benefit ratio of M4112** has been determined based on the following:

[figure not shown]
- CCI

CCI

- CCI

- CCI

- CCI

**The following potential risks of M4112 are**

1. Gastrointestinal intolerance including ulceration, bleeding with anemia and inflammation of gastric mucosa.
2. Liver toxicity either due to liver hypertrophy or direct liver lesions.
3. QT/QTc prolongation.
4. Inhibition/autoinduction of CYP3A4.
5. irAEs/autoimmune disorders.

Gastro-intolerance including ulceration and inflammation of gastric mucosa is a potential risk for M4112. The symptoms of gastrointestinal intolerance (nausea, vomiting, and diarrhea etc.) will be closely monitored, reported, and investigated. Discontinuation/interruption of treatment will be recommended for higher grade (Grade  $\geq 3$ ) events.

Liver toxicity is the clinically significant potential risk and relates to findings in animal toxicity studies. Subjects must be screened for potential impaired liver function or liver disease prior to treatment with a detailed medical history and clinical examination. All subjects enrolled in the clinical study should be counseled for early recognition and reporting of drug-related liver disease, and should be closely monitored in case of increased liver function tests and bilirubin (see Section 6.2.3).

QT/QTc prolongation is another important potential risk for M4112. A detailed medical history and medical examination to rule out a pre-existing heart disease and history of QT/QTc prolongation must be conducted (see Section 5.3.2). Subject inclusion and exclusion criteria and withdrawal criteria will exclude subjects deemed to be at risk for increase of QT. Time-matched triplicate digital ECG will be collected at Screening and at multiple time points (predose and postdose [Cmax]) in Cycle 1 and subsequent follow-up ECGs through all cycles. In M4112 monotherapy cohorts only (Part IA only), replicate ECGs (Holter) will also be collected on Days 1 and 15 of Cycle 1 for exposure-QTc analysis. Treatment modification guidance is described in Section 6.2.3.

M4112 is a sensitive substrate to CYP3A4 and it cannot be excluded that it inhibits or induces CYP3A4 to a clinically relevant extent. Strong inhibitors or inducers of CYP3A4 and drugs with a narrow therapeutic index, which are predominantly metabolized by CYP3A4, should be discontinued 7 days prior to treatment and avoided during treatment.

Subjects treated with M4112 should also be monitored for potential irAEs, which may first manifest after weeks of treatment. Such events may consist of persistent rash, diarrhea and colitis, autoimmune hepatitis, arthritis, glomerulonephritis, cardiomyopathy or uveitis and other inflammatory eye conditions. Risk management guidance is provided in Section 6.5.5.3.

No embryo-fetal toxicity study have been performed to date, therefore effects on pregnancy cannot be excluded, pregnancy and lactation are excluded from the study. Highly effective contraception must be used for men and women of childbearing potential (Section 5.3.1 and Section 5.3.2).

**Liver toxicity and irAEs will be considered AESIs for M4112 requiring expedited reporting from the Investigator to the Sponsor within 24 h of learning of its occurrence.**

CCI

CCI

CCI

Instructions for treatment interruption/discontinuation or modification of infusion-related reactions/hypersensitivity will be provided to investigators as well as guidance for medical management (Table 8).

CCI [REDACTED]. Inclusion criteria for the study will require adequate entry hemoglobin value. Respective hematological parameters will be monitored every week during the 1st cycle of dose escalation phase. Treatment modification, interruption, and discontinuation rules, depending on severity, will be provided. CCI [REDACTED]

CCI

CCI

